11.3.2 Macroscopic urinalysis

Quantitative urinalysis parameters will be summarized in the same manner as hematology and blood chemistry parameters. Response categories are negative, 1+, 2+, and 3+ for the qualitative urinalysis parameters occult blood, leukocytes, glucose, protein, and ketones and negative and positive for nitrates. Outcome values for these parameters are mapped to the levels Negative, 1+, 2+, and 3+ as follows for purposes of summary tables and the determination of PCST:

Category	Definition
Negative	“Negative”, “NEGATIVE”, or other outcomes that clearly reflect a negative finding
1+	“1+”, “+”, “Trace”, “TRACE”, or other outcomes that clearly reflect trace amount
2+	“2+” or “++”
3+	“3+”, “+++”, or other outcomes that clearly reflect the data above 3+ (eg, “4+”, “5+” etc) or more than 4 plus signs (eg, “++++”, “+++++”etc)

For qualitative urinalysis parameters (occult blood, leukocytes, glucose, protein, ketones, and nitrates), the number and percentage of subjects with each response category will be summarized for Baseline, Study Entry, each scheduled visit during the Evaluation Period for which urinalysis parameters were scheduled to be assessed, Last Value, EDV, and FV. Percentages for each parameter will be relative to the number of subjects with a result at each time point.

For occult blood, leukocytes, glucose, protein, ketones, and nitrates, the number and percentage of subjects with an on-treatment PCST value, PCST low value, and PCST high value will be summarized. This summary will consider all assessments after the first dose of BRV and prior to or on the date of the last dose of BRV. Percentages will be relative to the number of subjects with an on-treatment assessment.

Additionally, for occult blood, leukocytes, glucose, protein, ketones, and nitrates, the number and percentage of subjects with a PCST value, PCST low value, and PCST high value will be summarized for Baseline, Study Entry, each visit during the Evaluation Period for which laboratory parameters were scheduled to be assessed, EDV, Last Value, and FV. Percentages for each parameter and time point will be relative to the number of subjects with a value at that time point.

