- Male: $\text{Cr Cl mL/min} = [(140 - \text{age}) \times \text{body weight}] / [72 \times \text{serum creatinine (mg/dL)}]$
- Female: $\text{Cr Cl mL/min} = [(140 - \text{age}) \times \text{body weight}] / [72 \times \text{serum creatinine (mg/dL)}] \times 0.85$

The result of the calculated creatinine clearance will be provided by the central laboratory. Urine pregnancy tests should be used at any time during the study if a pregnancy is suspected.

Laboratory safety assessments at the EV will be taken from the last visit of N01358 or N01258 and do not need to be recorded on the CRF. Thereafter, laboratory safety assessments will be performed at the FEV, YEV, Last Evaluation Period Visit, and EDV. In addition, liver function tests will be performed at MEVs (Visit 4 and Visit 6) during the first year. Endocrinology (TSH) measurements will be performed at YEVs only. Laboratory assessments will also be mandatory at the FV, except if the FV follows an EDV where laboratory results were normal.

Results for hematology, blood chemistry, urinalysis, endocrinology, and pregnancy tests will be provided by fax to the Investigator within 72 hours after sample receipt. Results will be reported by the central laboratory to the Investigator as exact values, with a flag to those values that are outside the therapeutic range.

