11.3.3 Endocrinology parameters

Endocrinology parameters will be summarized in the same manner as hematology and blood chemistry parameters.

Observed values for each planned endocrinology parameter will be summarized for Baseline, EV, each scheduled visit during the Evaluation Period for which the parameter was assessed,

Last Value, EDV, and FV. Change from Baseline will be summarized for all post-Baseline time points including EV.

The number and percentage of subjects with an on-treatment potentially clinically significant treatment-emergent (PCST) value, PCST low value, and PCST high value will be summarized for each planned endocrinology parameter. All scheduled and unscheduled endocrinology assessments after the day of first dose of BRV and prior to or on the day of last dose of BRV across all study periods will be considered. Percentages for each parameter will be relative to the number of subjects with at least 1 result within this time period.

Additionally, the number and percentage of subjects with PCST value, PCST low value, and PCST high value will be summarized for endocrinology parameters for EV, each visit during the Evaluation Period for which endocrinology parameters were scheduled to be assessed, EDV, and Last Value. Percentages for each parameter and time point will be relative to the number of subjects with a result at that time point.

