13.3.3 Urinalysis

Qualitative urine parameters are generally reported by a descriptive score, which differs among laboratories. For data analysis purpose, a four-point scale is used. Five-point, six-point, or seven-point scales will be collapsed into a four-point scale first. A value is considered possibly clinically significant treatment emergent abnormal if an upward shift of at least 2 degrees from the baseline occurs under investigational treatment. To collapse the results in a five-point scale into a four-point scale, the lowest two positive results will be combined (see example below). For results reported with a scale of more than five-point, please consult your study physician for how to collapse into four-point scale.

Original Five-point Scale	Four-point Scale
Negative/None	Negative/None
Trace/Rare/Mild/A Few	Trace/1+/Rare/Mild/A Few
1+	
2+/Mod	2+/Mod
3+/Sev	3+/Sev

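### As written, the nitrite PCST row in the urinalysis summary is 0% by construction or undefined; secondarily, the planned TSH PCST summaries have no criterion

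*SAP*

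**What the plan says.** **Nitrite.** SAP 11.3.2 gives four ordered levels to occult blood, leukocytes, glucose, protein and ketones, but only two to the sixth parameter: "negative and positive for nitrates". Protocol 10.5.1 lists the test as nitrites; I take the two terms to mean the same test. The SAP continues: "Outcome values for these parameters are mapped to the levels Negative, 1+, 2+, and 3+ as follows for purposes of summary tables", and names PCST determination as a further purpose of that mapping. In the mapping table a single plus sign goes to 1+, along with trace results and "other outcomes that clearly reflect trace amount". Positive appears in no row.

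The section then plans, on treatment and again by visit: "For occult blood, leukocytes, glucose, protein, ketones, and nitrates, the number and percentage of subjects with an on-treatment PCST value", with low and high counts alongside.

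The only urinalysis criterion is in SAP 13.3.3: "For data analysis purpose, a four-point scale is used". A result counts as PCST "if an upward shift of at least 2 degrees from the baseline occurs under investigational treatment". The collapsing instructions there deal with scales of five points or more and are silent on a two-point result.

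**TSH.** SAP 11.3.3 says: "PCST low value, and PCST high value will be summarized for each planned endocrinology parameter". It plans these on treatment and by visit. The laboratory table in Protocol 10.5.1 shows TSH as the only endocrinology test, and the text adds: "Endocrinology (TSH) measurements will be performed at YEVs only". SAP 13.3 has four subsections: 13.3.1 hematology, 13.3.2 blood chemistry (mis-headed as hematology), 13.3.3 urinalysis, and 13.3.4 vital signs and body weight. The SAP table of contents lists nothing after 13.3.4.

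**The concern.** A row that cannot take any value but zero looks, in a finished safety table, just like a row that was observed to be zero. A reader of the urinalysis PCST summary has no way to tell that the nitrite entry was fixed by the scale and not by the subjects. If the programmer notices that Positive is unmapped and assigns it a level, the row depends entirely on a coding choice that the SAP does not record.

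The TSH gap is of a different kind: the rule is missing, where for nitrite it fails. Someone would have to choose low and high limits in an open-label study whose data have already been summarized for interim submissions (SAP 4.3). Protocol Amendment 1 says that yearly TSH was added at a regulatory agency's request, which is a reason to have its abnormality rule written down.

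**Working it through.** The plan states no figure to reproduce. The check is an enumeration of possible shifts and a search of the criteria lists.

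**Step 1: which shifts can qualify.** Number the levels of a k-level scale in order and define shift = on-treatment rank − baseline rank. The largest shift is k − 1. The number of baseline/on-treatment pairs with a shift of 2 or more is (k − 1)(k − 2)/2.

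| Scale | Largest shift | Qualifying pairs |
|---|---|---|
| Four levels (k = 4) | 3 | 3 × 2 / 2 = 3 of 16: Negative to 2+, Negative to 3+, 1+ to 3+ |
| Two levels (k = 2) | 1 | 1 × 0 / 2 = 0 of 4 |

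The rule works for the five four-level parameters. On the two levels stated for nitrites, it can flag nobody.

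**Step 2: does the mapping rescue it?** SAP 11.3.2 gives no level for Positive, so each possibility is tried.

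| Positive coded as | Shift from Negative | PCST? |
|---|---|---|
| 1+ (the level the table gives a bare plus sign) | 1 | No |
| 2+ | 2 | Yes |
| 3+ | 3 | Yes |
| Not coded | None defined | Undefined |

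The reading closest to the table, 1+, still gives 0%. Coding to 2+ or 3+ would flag every change from negative to positive, but nothing in the SAP directs that.

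**Step 3: what the row could miss.** The documents give no nitrite conversion rate. Assume, for illustration only, that 2% to 10% of subjects go from negative to positive. Take 650 to 820 subjects (Protocol 12.9: 650 to 720 from N01358 and up to 100 from N01258; 720 + 100 = 820), all with both assessments. That is 650 × 0.02 = 13 to 820 × 0.10 = 82 subjects. A negative-to-positive rule would flag all of them; the 2-degree rule on two levels flags 0.

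**Step 4: TSH.** SAP 13.3.1 lists 10 parameters and 13.3.2 lists 21. None of these 31 is TSH. Section 13.3.3 covers qualitative urine results, and 13.3.4 covers pulse rate, systolic and diastolic blood pressure, and weight. No low or high limit for TSH can be derived from the SAP. Where definitions are kept outside the SAP, it says so (AED search criteria in 6.4, AEs of interest in 11.2.2). It does not say so for PCST limits.

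**The case against.** The strongest reply on nitrite is that PCST is determined after mapping to four levels, so the two-level description is not the scale to which the rule applies. That stands in part: it is why the row must be called 0% or undefined, and why an unqualified 0% would say too much. It does not remove the defect, because Positive has no place in the mapping and its nearest listed notation gives a shift of 1.

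A reader might infer several stronger points that the documents do not support:

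- **That the report would show no nitrite abnormality at all.** SAP 11.3.2 separately plans the number and percentage of subjects in each response category, nitrates included, at Baseline, Study Entry, scheduled visits, Last Value, EDV and FV. Nitrite-positive percentages will be visible.
- **That the whole urinalysis PCST table fails.** Nitrite is one of six parameters, and the other five have a workable scale.
- **That the empty low columns for urinalysis are a further fault.** An upward-only rule does leave them empty, but the same layout is planned for hematology and chemistry, where several criteria are also one-sided (high only for AST, ALT, creatinine and total bilirubin; low only for hematocrit and hemoglobin). This is harmless table layout.
- **That TSH should be shown as a shift from baseline.** SAP 3.3 and 11.3.3 refer to an endocrinology baseline. However, the protocol measures TSH only at yearly visits, and its list of laboratory data carried over from the earlier studies (footnote c of Table 5-1; Section 8.1) does not include endocrinology. A baseline TSH may not exist.

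It is also fair to say that the TSH gap is closer to missing detail than to error. Observed TSH values and changes from Baseline remain planned.

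**Conclusion.** The concern holds in a narrow form. The nitrite PCST entry, on treatment and by visit, cannot inform: it is 0% on the two levels stated and also if Positive is read as 1+, and it is undefined if Positive is left unmapped. This rests on the SAP text alone and on nitrates and nitrites being the same test. It would fail only if Positive were coded 2+ or 3+, which the SAP does not say.

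The TSH PCST summaries lack a criterion altogether. As TSH is the only planned endocrinology parameter, that affects every endocrinology PCST count.

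The size is small. Laboratory tests are among the other safety variables (SAP 2.2.1.2); the primary ones are TEAEs, withdrawals due to AEs, and SAEs. No collected data are lost and no primary conclusion changes. The correction is worth making because it is cheap and because a zero fixed by definition should not sit in a safety table as if it had been observed.

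**What to change.** 1. **SAP 13.3.3:** add that nitrite PCST means negative at baseline and positive on treatment. Alternatively, remove nitrates from both PCST summaries in 11.3.2 and rely on the category counts. The first option needs only the baseline and on-treatment nitrite results that 11.3.2 already plans to tabulate.
2. **SAP 13.3, before database lock:** add a TSH entry that defines low and high on-treatment values by the central-laboratory reference range. Protocol 10.5.1 has that laboratory flag out-of-range results, so I assume that the range is available. Alternatively, delete the PCST paragraphs from 11.3.3 and keep observed values and changes from Baseline.

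The cost is a few lines of SAP text and the matching table specifications, with no new data collection.

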11.3.3 Endocrinology parameters

Endocrinology parameters will be summarized in the same manner as hematology and blood chemistry parameters.

Observed values for each planned endocrinology parameter will be summarized for Baseline, EV, each scheduled visit during the Evaluation Period for which the parameter was assessed,

Last Value, EDV, and FV. Change from Baseline will be summarized for all post-Baseline time points including EV.

The number and percentage of subjects with an on-treatment potentially clinically significant treatment-emergent (PCST) value, PCST low value, and PCST high value will be summarized for each planned endocrinology parameter. All scheduled and unscheduled endocrinology assessments after the day of first dose of BRV and prior to or on the day of last dose of BRV across all study periods will be considered. Percentages for each parameter will be relative to the number of subjects with at least 1 result within this time period.

Additionally, the number and percentage of subjects with PCST value, PCST low value, and PCST high value will be summarized for endocrinology parameters for EV, each visit during the Evaluation Period for which endocrinology parameters were scheduled to be assessed, EDV, and Last Value. Percentages for each parameter and time point will be relative to the number of subjects with a result at that time point.

11.3.4 Microscopic urinalysis

In microscopic urinalysis, a small sample of urine is centrifuged to remove the liquid. The sediment is then examined under a microscope. The number and percentage of subjects with a microscopic urinalysis finding will be summarized. All scheduled and unscheduled assessments after the day of first dose of BRV will be considered. Percentages will be relative to the number of subjects with at least 1 on-treatment microscopic assessment.

Additionally, the number and percentage of subjects with a microscopic finding will be summarized for Baseline, Study Entry, and each visit during the Evaluation Period for which urinalysis parameters were scheduled to be assessed, Last Value, EDV, and FV. Percentages for each parameter and time point will be relative to the number of subjects who had a microscopic assessment at that time point.

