3.2.4 Study periods

The Baseline Period for N01379 corresponds to the Baseline Period of the previous studies, and is defined for seizure outcomes and direct cost parameters. The Baseline Period is defined as study days on or after the date of Visit 1 and prior to the date of Visit 2 for N01258 and study days on or after the date of Visit 1 and prior to the date of Visit 3 for N01358.

The study is divided into 3 periods: Evaluation Period, Down-Titration Period, and Post-Treatment Period. A subject is classified as “discontinued” if the subject has a termination case report form (CRF) or has an early discontinuation visit (EDV). A subject is classified as “completed” if this subject completes the full extent of the study as defined in the protocol at database lock.

A “discontinued” subject can be potentially slotted into the 3 periods of the study. The following algorithms will be used to slot the subject appropriately into the Evaluation Period, Down-Titration Period, and Post-Treatment Period.

- For Evaluation Period, the start date is the date of first dose of BRV, and the following algorithm is used to determine the end date:
 - If the subject enters the Down-Titration Period, then the date of EDV is the end date;
 - If the subject does not enter the Down-Titration Period but meets 1 of the following criteria, the Evaluation Period ends on date of last dose of BRV:
 - Without an EDV but having a termination CRF,
 - With an EDV and having a termination CRF,
 - With an EDV and the date of EDV prior to the database lock date and having no termination CRF.

- A subject is considered entering Down-Titration Period only if the subject has an EDV and at least 1 dose of study drug after the date of EDV, the start date of Down-Titration Period is set as 1 day after the date of EDV, and the Down-Titration Period ends on date of last dose of BRV. A subject without an EDV but having a termination CRF or with an EDV but without any dosing of study drug after the EDV will not have the Down-Titration Period, and no artificial Down-Titration Period will be created for analysis.
- A subject is considered entering the Post-Treatment Period if the subject has at least 1 contact (scheduled visit, unscheduled visit, or telephone contact) after the date of last dose of BRV. The Post-Treatment Period starts 1 day after date of last dose of BRV irrespective of entering the Down-Titration Period, and there is no end date.

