3.2.7 Exposure duration and exposure duration cohorts

At the final analysis, the overall duration of exposure (or On Treatment Period) will be calculated as the date of last dose of BRV minus the date of first dose of BRV plus 1 day.

Each subject will be classified into one or more of the following exposure duration cohorts based on the duration of BRV exposure as calculated above:

All subjects	≥1 day
≥3 months	≥90 days
≥6 months	≥180 days
≥12 months	≥360 days

This categorization will continue in 6-month increments past 12 months up to a time point that will be determined based on cumulative exposure at the time of the database lock.

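### SAP 11.3.4: the overall microscopic urinalysis percentage has an open-ended numerator window and an on-treatment denominator, so it can be overstated

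*SAP*

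**What the plan says.** SAP Section 11.3.4 plans two summaries of microscopic urinalysis findings. The first is an overall number and percentage of subjects with a finding. Its numerator rule is "All scheduled and unscheduled assessments after the day of first dose of BRV will be considered". Its denominator rule is "Percentages will be relative to the number of subjects with at least 1 on-treatment microscopic assessment". The second is a by-visit summary, including the Final Visit, with each percentage taken over the subjects who had a microscopic assessment at that time point.

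SAP Section 3.2.7 fixes what on treatment means. For overall duration of exposure it states "or On Treatment Period) will be calculated as the date of last dose of BRV minus the date of first dose of BRV", plus one day. Section 3.2.1 adds that the last dose is the last one taken in any study period, so down-titration is on treatment. What follows is off treatment: "The Post-Treatment Period starts 1 day after date of last dose of BRV irrespective of entering the Down-Titration Period, and there is no end date" (SAP Section 3.2.4).

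The section on macroscopic urinalysis just before it uses a closed window: "This summary will consider all assessments after the first dose of BRV and prior to or on the date of the last dose of BRV". The endocrinology section also closes the window, "after the day of first dose of BRV and prior to or on the day of last dose of BRV across all study periods", and ties its denominator to it: "Percentages for each parameter will be relative to the number of subjects with at least 1 result within this time period".

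**The concern.** The numerator sentence in Section 11.3.4 has a start and no end, while the denominator sentence is confined to treatment. The two halves of the fraction therefore cover different periods.

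If the table is programmed as written, there are two consequences. Findings that first appear after BRV has stopped are reported as part of an on-treatment percentage. And the numerator need not be a subset of the denominator. Long-term safety is the primary objective and urinalysis is a listed safety variable, so an on-treatment percentage should contain on-treatment data only. Two programmers could also read the paragraph differently and produce different tables.

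**Working it through.** The documents give no figure for this table, so there is nothing to reproduce. The check compares the windows, asks whether off-drug samples can arise, and sets out the arithmetic of the mismatch.

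**1. Windows side by side (overall summaries only)**

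| SAP section | Numerator window ends | Denominator |
|---|---|---|
| 11.3.1 Hematology and chemistry | Last dose | On-treatment assessment |
| 11.3.2 Macroscopic urinalysis | Last dose | On-treatment assessment |
| 11.3.3 Endocrinology | Last dose | Result in the same window |
| 11.3.4 Microscopic urinalysis | **No end stated** | On-treatment assessment |
| 11.4.1 Vital signs | Last dose | On-treatment assessment |
| 11.4.2 ECG | Last dose | On-treatment assessment |

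Section 11.3.4 is the only one of the six without an upper bound. The Last Value row in its own by-visit table stops at the last dose, under Section 3.2.6.

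**2. Do off-drug urine samples exist?** Yes, by design.
- Protocol Section 5.1.1 places the Final Visit after a Posttreatment Period of 2 to 4 weeks.
- Protocol Section 8.8 includes urinalysis at the Final Visit unless it follows an Early Discontinuation Visit with normal laboratory results.
- Protocol Section 10.5.1 (footnote b to the laboratory table) has microscopy done on every sample.
- SAP Section 3.2.4 foresees subjects with an Early Discontinuation Visit and no dosing after it. If that visit falls after the last dose, its urine sample is off drug too.

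**3. Can a subject be in the numerator but not the denominator?** Yes, in a narrow case. After entry, the first scheduled urinalysis is at Month 2 (Protocol Sections 5.3 and 8.2), because the Month 1 visit has none (Section 8.3). A subject who stops before Month 2 and is first sampled after the last dose has no on-treatment assessment. A finding in that sample would still meet the numerator rule.

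**4. Arithmetic.** Let D be the subjects with at least one on-treatment assessment, *a* those with an on-treatment finding, and *b* those whose only finding is off drug, whether or not they belong to D.

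- As written: (a + b) / D
- Matched on-treatment percentage: a / D
- Excess: b / D, which is zero or positive

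An illustration with assumed values D = 700 and a = 140, none of them estimates:

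| Assumed b | As written | Matched | Excess |
|---|---|---|---|
| 0 | 140/700 = 20.0% | 20.0% | 0 points |
| 7 | 147/700 = 21.0% | 20.0% | 1 point |
| 35 | 175/700 = 25.0% | 20.0% | 5 points |

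The excess simply follows the value chosen for *b*, and the documents do not give one.

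**The case against.** The strongest reply is that the mismatch is an omitted clause, not an intention. SAP Section 3.1 says denominators are generally based on subjects with an assessment in the interval being summarized. The denominator sentence says on-treatment, and every parallel section closes at the last dose. A careful programmer might infer one matched window, and then nothing is overstated. That is plausible as to intent, and the SAP nowhere says that off-drug samples should count. But the rule in Section 3.1 is a general default, and the specific sentence in Section 11.3.4 says all assessments after first dose. Followed as written, it gives the mismatch.

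The reply on size also stands. Subjects who move to commercial BRV, another BRV study or an access program have no Final Visit. Laboratory tests at the Final Visit may be skipped after a normal Early Discontinuation Visit, so those tested are likely to include more subjects with earlier abnormal results. Some of these will already have an on-treatment finding and add nothing to *b*. On-treatment urinalysis is repeated at Months 2, 6, 12, 18 and onward, so only a subject with no finding at any of these can add one later. The numerator-only case is confined mainly to very early dropouts.

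Post-treatment data are not foreign to this SAP either: the main adverse event summaries combine all three study periods. Widening the denominator to every subject assessed after the day of first dose would also cure the arithmetic, but the result would no longer be an on-treatment percentage.

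A reader might also infer that the open window is what prevents this table from being read beside the other laboratory tables. The documents do not support that. Those on-treatment tables count potentially clinically significant treatment-emergent values; for qualitative urinalysis, this is an upward shift of at least 2 degrees from baseline (SAP Section 13.3.3). Section 11.3.4 counts any microscopic finding, so the rates would differ in meaning even with identical windows.

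**Conclusion.** The point holds as a minor defect in a stated rule. Read literally, Section 11.3.4 lets off-drug findings into an on-treatment percentage and allows a subject in the numerator who is not in the denominator. Compared with a matched on-treatment figure, the percentage can only rise or stay the same.

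It is tempting to go further and say that the percentage is overstated by several points. The documents do not support that. They give neither the number of off-drug urine samples nor the rate of first findings in them, and the features noted above point towards a small effect that may be near zero. The conclusion rests on the literal wording and on on-treatment meaning first to last dose.

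The scope is one descriptive table. The by-visit summary in the same section is sound, Final Visit findings are already visible there, and no hypothesis is tested.

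**What to change.** In SAP Section 11.3.4, end the numerator window of the overall summary at the last dose, for example by adding *and no later than the date of the last dose of BRV*, or by reusing the closing clause of Section 11.3.2. Numerator and denominator then share one window, consistent with Sections 11.3.1 to 11.3.3, 11.4.1 and 11.4.2. Leave Final Visit findings to the by-visit table.

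The cost is one SAP clause and the matching date condition in one table program. No data collection changes.
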